QIDS-SR16, DLQI, SF-12, WPAI:PSO, HEOR		X			X	X		X	X	X	
Photography											

Evaluation	Screening Period ¹	Double-Blind Titration Period (5 weeks)		Double-Blind Treatment Period					ETV and EOS Safety Follow-up Period ²		Un-scheduled Visit ³
	Weeks -4 to 0	Baseline visit	Week 4	Week 8	Week 12	Week 16	Week 20	Week 24	Early Termination Visit	Week 25 (1 Week After Week 24/ETV)	
Study Day	Day -28 to Day -1	Day 0	Day 28 (± 3 days)	Day 56 (± 3 days)	Day 84 (± 3 days)	Day 112 (± 3 days)	Day 140 (± 3 days)	Day 168 (± 3 days)	-	175 (+3 days)	
Visit Number	1	2	3	4	5	6	7	8	ETV	9	UNS
Photography (4 sites, 5 subjects/site)		X			X	X		X			

- The Screening Period can only be extended on a case-by-case basis if a longer than 4 weeks' washout is required; however, the Investigator will need to obtain approval from the Medical Monitor in advance of the extension.
- Subjects who permanently discontinue the study drug for any reason or who withdraw from the study prematurely prior to the end of the Double-Blind Treatment Period should undergo the ETV followed by the EOS Safety Follow-up Period Visit. In the event that the ETV or Week 24 Visit occurs > 1 week following the last dose of the study drug, the EOS Safety Follow-up Visit may not be required. If necessary, the Investigator may decide to extend the EOS Safety Follow-up Visits beyond 1 week to monitor recovery of safety parameters (eg, lymphopenia).
- Table includes recommended. Un-scheduled procedures, whichever are applicable, should be performed at the Investigator's discretion.
- Initial eligibility assessment.
- Mandatory confirmatory eligibility assessment.
- Study drug will be dispensed as per the titration schedule described in Double-Blind Titration section.
- Laboratory assessments include routine laboratory evaluations (i.e., chemistry, hematology, and urinalysis), and assessment of lipid panel and hsCRP
- Blood collection for lymphocyte subset & Ab titer study can be collected at any study visit if the subject shows signs of progressive multifocal leukoencephalopathy (PML).
- SAEs will be collected following the signing of the Informed Consent Form; AEs will be collected following the first dose of study drug.

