## 12.4 Study Medication Exposure and Compliance

The following exposure and compliance parameters will be summarized by treatment group and study period (overall, titration, and treatment as applicable) using descriptive statistics:

- Total number of days exposed to study medication, defined as date of last dose of study drug during the study minus date of first dose of study drug plus 1.
- Total number of tablets taken during the titration period (Week 1 – 5), defined as number of dispensed tablets from blister wallets minus number of returned tablets from blister wallets.
- Total number of tablets taken during the treatment period (Week 6 – 24), defined as total number of dispensed tablets from bottles minus total number of returned tablets from bottles.
- Number of tablets per bottle taken during the treatment period (Week 6 – 24), defined as number of dispensed tablets per bottle (total of 4 bottles per visit) minus number of returned tablets per bottle.
- Total number of tablets taken, defined as the summation of number of tablets taken during the titration and treatment period.
- Percent compliance will be calculated as the number of tablets taken divided by the expected number of tablets, defined for the titration period, treatment period, and overall. The expected number of tablets are as following:

Period	Number of Tablets Dispensed Per Dosing Regimen	Expected Total Number of Tablets
Titration (Week 1 – 5)	Week 1 – 4: 28 per week Week 5: 35 per week	$28*4 + 35 = 147$
Treatment (Week 6 – 24)	42 per week	$42*19 = 798$
Overall (Week 1 – 24)		945

- Subject compliance, defined as 80% - 120% (inclusive) in percent compliance. If the percentage of study medication compliance is unknown, the subject is assumed to be non-compliant with study medication. Subject compliance is summarized by periods and overall. Overall compliance will be the main determinant of compliance.
- Average daily dose of IP received can be calculated as the number of tablets divided by the number of days exposed to study medication. The average daily dose of IP received by each subject will be summarized by treatment group using summary statistics for the overall period.

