## **12.9 Safety Analysis**

## 12.9.1 Adverse Events

AE terms will be coded using MedDRA dictionary. A treatment-emergent AE (TEAE) is defined as an AE that starts after the first dose of study medication through 5 days after the last dose. If relationship to treatment is missing, the event will be conservatively considered as being related to study drug. If severity is missing, a separate category of missing severity will be included in the summary table, and no imputation of severity will be performed. Through the data cleaning process, all attempts will be made to avoid missing values for relationship and severity.

All AEs will be presented in a by-treatment and by-subject listing, detailing the verbatim term given by the investigator, the preferred term (PT), system organ class (SOC), onset date and time, end date and time, intensity, outcome, relationship to study drug/treatment, action taken with study drug/treatment, other action taken to treat the event, seriousness and criteria for seriousness. Serious AEs (SAEs) and TEAEs leading to study discontinuation will also be presented in a separate listing. Deaths and non-fatal SAEs will be listed by subject and tabulated by PT.

Each TEAE will be identified as titration period AE or treatment period AE according to the following rules:

- PPC-06 400 mg QD:
  - Any TEAE starting before Day 15 is considered as a titration period AE
  - Any TEAE starting on or after Day 15 is considered as a treatment period AE
- PPC-06 400 mg BID, PPC-06 600 mg BID:
  - Any TEAE starting before Day 36 is considered as a titration period AE
  - Any TEAE starting on or after Day 36 is consider as a treatment period AE
- Placebo BID:
  - No study period will be further designated for this group. They should match equivalent phases to calculate therapeutic effect for eg: for 400 mg it should be Day 15 and >15 days, for other doses it should be Day 36 and >36 days.

An overall summary of AEs will be presented by treatment and overall, for the titration period, treatment period, and overall. The summary will include the total number of events, frequency counts and percentages, and exposure-adjusted incidence rate for:

- Any AE
- Any TEAE
- Any serious TEAE
- Any treatment-related TEAE, including definitely, probably, and possibly related
- Any TEAE leading to study drug discontinuation
- Any SAEs (non-Fatal)
- Any Deaths

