For the 3 arms receiving active treatment, exposure-adjusted incidence rate will be defined for both titration and treatment periods as number of subjects with AEs divided by total number of subject-days with exposure to study medication. Total number of subject-days with exposure in each period = sum of durations in days across all subjects in each period. Duration in each period is defined as following:

- PPC-06 400 mg QD:
  - Titration period = Number of days between date of first study application and the earlier of date of last study medication and Day 14 inclusive
  - Treatment period = Number of days between Day 15 and date of last study application inclusive
- PPC-06 400 mg BID, PPC-06 600 mg BID:
  - Titration period = Number of days between date of first study application and the earlier of date of last study medication and Day 35 inclusive
  - Treatment period = Number of days between Day 36 and date of last study application inclusive

Summaries of the incidence of TEAEs will be displayed by treatment according to the following:

- All TEAEs by SOC in alphabetical order and PT in descending order of frequency (the combined frequency in the three active treatments)
- All TEAEs by SOC, PT, and maximum severity (mild, moderate, or severe)
- All TEAEs by SOC, PT, and maximum causality (not related, related) to the study drug

At each level of summarization, a subject will be counted once if he/she reported one or more events. In the counts of subjects with TEAEs, each subject will contribute only once (maximum severity) regardless of the number of occurrences (events).

The severity of TEAEs and relationship to study drug will be summarized in a similar manner. For summaries of relationship to study drug, a subject will be classified according to the closest relationship. For summaries of TEAE severity, a subject will be classified according to the highest severity.

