Death				
<etc.>				
AEs Leading to Study Drug Discontinuation				
<etc.>				

Note: For each treatment, a subject will be counted once only within each AE category. TEAEs include all AEs starting or worsening after the first dose of study drug.

[1] Number of subjects with AEs divided by total number of subject-days with exposure to study medication, defined as sum of duration in days across all subjects during the study period.

Generated on XX/XX/XX:XXXX by SMYAE / Uses: XXXX / Reference: Listing XXXX

Table 14.3.1.2: Summary of Treatment-emergent Adverse Events  
by System Organ Class and Preferred Term in Descending Frequency  
Safety Population

System Organ Class Preferred Term	PPC-06 400 mg QD (N=XX)	PPC-06 400 mg BID (N=XX)	PPC-06 600 mg BID (N=XX)	Placebo (N=XX)
Subjects with any TEAE, n (%)	XX (XX.X)	XX (XX.X)	XX (XX.X)	XX (XX.X)
<< Adverse Event System Organ Class >>	XX (XX.X)	XX (XX.X)	XX (XX.X)	XX (XX.X)
<< Adverse Event Preferred Term >>	XX (XX.X)	XX (XX.X)	XX (XX.X)	XX (XX.X)
<< Adverse Event Preferred Term >>	XX (XX.X)	XX (XX.X)	XX (XX.X)	XX (XX.X)
<< Adverse Event Preferred Term >>	XX (XX.X)	XX (XX.X)	XX (XX.X)	XX (XX.X)
<< Adverse Event System Organ Class >>	XX (XX.X)	XX (XX.X)	XX (XX.X)	XX (XX.X)
<< Adverse Event Preferred Term >>	XX (XX.X)	XX (XX.X)	XX (XX.X)	XX (XX.X)
<< Adverse Event Preferred Term >>	XX (XX.X)	XX (XX.X)	XX (XX.X)	XX (XX.X)
<< Adverse Event Preferred Term >>	XX (XX.X)	XX (XX.X)	XX (XX.X)	XX (XX.X)

Note: Counts reflect numbers of subjects reporting one or more adverse events that map to MedDRA system organ class or preferred term. A subject may be counted once only in each row of the table.

Generated on XX/XX/XX:XXXX by SMYTEAEPT / Uses: XXXX / Reference: Listings XXXX

<Programming Note: sort by SOC in alphabetical order and PT in descending order of the combined frequency in the three active treatments>

Table 14.3.1.3: Summary of Treatment-emergent Adverse Events  
 by System Organ Class, Preferred Term, and Maximum Severity  
 Safety Population

System Organ Class Preferred Term	Severity	PPC-06 400 mg QD (N=XX)	PPC-06 400 mg BID (N=XX)	PPC-06 600 mg BID (N=XX)	Placebo (N=XX)
Subjects with any TEAE, n (%)	Total	XX (XX.X)	XX (XX.X)	XX (XX.X)	XX (XX.X)
	Mild	XX (XX.X)	XX (XX.X)	XX (XX.X)	XX (XX.X)

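### The exposure-adjusted adverse-event rate counts events over a longer window than its first-to-last-dose denominator, most clearly in the non-fatal SAE row

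*SAP*

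**What the plan says.** SAP 12.9.1 lists the rows of the overall AE summary (Tables 14.3.1.1.1 to 14.3.1.1.3) and asks for events, counts, percentages and an exposure-adjusted rate on each. Some rows are limited to treatment-emergent events. Three are not: any AE, any deaths, and a row that begins "Any SAEs (non-Fatal". Any serious TEAE is a separate row, so the natural reading is that the SAE row takes all non-fatal SAEs.

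**Denominator.** For the titration and treatment periods in the active arms, SAP 12.9.1 defines the rate as "number of subjects with AEs divided by total number of subject-days with exposure to study medication". The overall rate is defined only in the footnote to Table 14.3.1.1.3, where the subject-days are "defined as sum of duration in days across all subjects during the study period". SAP 12.4 defines days exposed as "date of last dose of study drug during the study minus date of first dose of study drug plus 1".

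**Numerator.** A footnote to Protocol Table 1-1 states: "SAEs will be collected following the signing of the Informed Consent Form; AEs will be collected following the first dose of study drug". A TEAE is "defined as an AE that starts after the first dose of study medication through 5 days after the last dose". AEs are also recorded at the follow-up visit (Protocol 7.2.5). Protocol 7.5.1.2 has AEs monitored for up to 30 days after treatment stops, without saying whether new events are collected for that long.

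**The concern.** A rate is interpretable when the events and the person-time come from the same window. Here an SAE during screening, or in the days after the last dose, can enter the numerator while those days are left out of the denominator. No sentence in either document aligns the two.

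The result is an upward bias that grows as time on drug shortens. With 50% dropout assumed, and dropout that may differ by dose through intolerance, arms with the same underlying hazard could show different rates. This is separate from whether exposure after a subject's first event should count, and correcting that would not remove it.

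The shells add an ambiguity. Only TEAEs are assigned to the titration or treatment period, yet both period tables carry the AE, SAE and death rows. Where a screening SAE belongs is undefined.

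**Working it through.** **The plan's own figure.** Protocol 4.1 gives a maximum study duration of about 29 weeks. Screening 4 + dosing 24 + follow-up 1 = 29 weeks, or 28 + 168 + 7 = 203 days. It reproduces. The documents give no SAE rate or exposure-adjusted rate to check.

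**Inputs.**
- Screening S: up to 28 days (Protocol 4.1). 14 days is an assumed shorter case.
- Post-dose days F: 7, or 10 with the +3-day window, assuming the last dose falls at the Week 24 or early termination visit; 30 if new events count throughout the monitoring period; 5 for TEAEs.
- Mean exposure E: 168 days for a completer. SAP 7 assumes 50% dropout but not its timing; spread evenly, E = 0.5 × 168 + 0.5 × 84 = 126.

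**Formula.** For rare events at constant hazard, overstatement = (S + E + F)/E − 1 = (S + F)/E.

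| Row | S | F | Completer, E = 168 | 50% even dropout, E = 126 |
|---|---|---|---|---|
| Non-fatal SAE | 28 | 7 | 35/168 = 20.8% | 35/126 = 27.8% |
| Non-fatal SAE | 28 | 10 | 38/168 = 22.6% | 38/126 = 30.2% |
| Non-fatal SAE | 14 | 7 | 21/168 = 12.5% | 21/126 = 16.7% |
| Non-fatal SAE | 28 | 30 | 58/168 = 34.5% | 58/126 = 46.0% |
| Deaths | 0 | 7 | 7/168 = 4.2% | 7/126 = 5.6% |
| TEAE rows | 0 | 5 | 5/168 = 3.0% | 5/126 = 4.0% |

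With earlier dropout (half leaving at a mean of Day 42), E = 0.5 × 168 + 0.5 × 42 = 105, and the TEAE figure is 5/105 = 4.8%.

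**Counting subjects, not events.** The SAP counts each subject once. Using 1 − exp(−ht) with 50% even dropout, S = 28 and F = 7, the overstatement is 27.5% if 2% of subjects would have an event in 24 weeks and 27.1% if 5% would. The simple formula is therefore adequate for SAEs. For common events it overstates: with S = 0 and F = 7, the 5.6% falls to 3.4% when 80% of subjects would have an event.

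**Between-arm effect.** Take two arms with the same hazard, S = 28 and F = 7. One has E = 105; the other has 25% even dropout, so E = 0.75 × 168 + 0.25 × 84 = 147. The false rate ratio is (1 + 35/105)/(1 + 35/147) = 1.333/1.238 = 1.08.

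**Period boundary.** A 400 mg BID subject takes the last dose on Day 33 and has an event on Day 37. This is a TEAE (33 + 5 = 38) and, starting after Day 35, a treatment-period event. Under SAP 12.9.1 the subject has no treatment-period exposure.

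**The case against.** The case for leaving this alone has several parts.

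- **Selection.** The AE tables use the Safety population, so a screening SAE counts only if the subject still passes the Baseline eligibility check and is dosed. Exclusion 9 removes unstable or significant illness at screening that the investigator judges an unacceptable risk. Constant hazard through screening ignores this. The point stands: the screening term is smaller than computed, by an unknown amount.
- **Scope.** A reader might infer that all three non-TEAE rows carry the full screening excess. They do not. A subject who dies before dosing is not in the Safety population, so the deaths row has only the post-dose part. Non-serious AEs are collected from first dose, so before dosing the any-AE row can gain only SAEs.
- **Importance.** Suppose an SAE hazard of 0.05 to 0.10 per year (an assumption). Then 100 subjects with a mean of 126 days contribute 12,600 days, or 34.5 years, and about 1.7 to 3.5 subjects with an SAE. The extra 35 days each add 3,500 days, or 9.6 years, and about 0.5 to 1.0 subject. A ratio of 1.08 cannot be seen against such counts, and no test of these rates is planned. This stands too.
- **Visibility.** The serious TEAE row excludes pre-dose events, and Listing 16.2.7.2 shows each SAE's onset day and treatment-emergent flag. A careful reader could find a pre-dose SAE, but the printed rate would still be wrong.

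None of this aligns the two windows.

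**Conclusion.** The mismatch is real and minor. It matters most for the non-fatal SAE row: about 21-23% for completers and 28-30% with 50% evenly spread dropout, given constant hazard, 28-day screening and 7 to 10 days of follow-up; about 13-17% with 14-day screening and 7 days. The other rows are affected far less, with 3-5% on the TEAE rows at most and less where events are common.

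A reader might take roughly 30% as a ceiling. The documents do not support that. The figure is too high to the extent that subjects with a screening SAE are not dosed. It is too low (35-46% with 28-day screening) if new SAEs count for 30 days after the last dose, which the documents leave open. Dropout timing and average screening length are not given either.

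Nor do the documents support inferring that an arm with earlier dropout would show a materially misleading SAE rate against placebo. The illustrative distortion is a factor of about 1.08 in a descriptive table, and no primary conclusion depends on it.

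**What to change.** In SAP 12.9.1 and the shells of Tables 14.3.1.1.1 to 14.3.1.1.3:

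- Give the exposure-adjusted rate only for the TEAE rows: any, serious, treatment-related, and leading to discontinuation.
- Define at-risk time as first dose to the earlier of last dose plus 5 days and last contact. Under constant hazard this removes the window bias. Limiting the numerator alone would leave 3-4%.
- Split that time between titration and treatment at the cut used for the events: Day 15 for 400 mg QD, Day 36 for the BID arms, and each in turn for the matching placebo columns. The Day 33 example then contributes Days 36 to 38 to the treatment period.
- Put this definition in the Table 14.3.1.1.3 footnote in place of the loose reference to the study period, and add the 5-day limit to that table's TEAE note, which has no end date.
- Report any AE, non-fatal SAEs and deaths as counts and percentages only, with pre-dose SAEs shown separately.

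The cost is SAP wording and three shells, with no new data. The downside is that fewer rows carry a rate.

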## **12.9.2 Clinical Laboratory Testing**

Clinical laboratory values will be reported as complete listings of individual subject data. All laboratory values will be classified as normal, low, or high based on normal ranges supplied by the laboratory. Subjects with values outside the normal range will be flagged and summarized using shift tables. A separate listing and table will identify and summarize subjects with markedly abnormal values. For quantitative measures, observed and changes in clinical laboratory values will be analyzed descriptively by time of collection and treatment group.

Additionally, lymphocyte counts will be summarized by clinical response of PASI-50 and PASI-75 (Yes/No) at Week 24. Lymphocyte counts and hs-CRP will also be plotted against PASI scores by visit and treatment. The correlation coefficient will be reported.

### 12.9.3 Vital Signs

Change in vital sign data will be classified as normal, low, high, based on a reference range. Observed and changes in vital sign parameters will be analyzed descriptively by visit and treatment group. Subjects with markedly abnormal changes will be listed and tabulated separately.

	Low	Normal	High	Abnormal (Absolute) Change from Baseline	Markedly Abnormal (Absolute) Change from Baseline
SBP	<90 mmHg	90-140 mmHg	>140 mmHg	≥ 20 mmHg	≥ 40 mmHg
DBP	<50 mmHg	50-90 mmHg	>90 mmHg	≥ 10 mmHg	≥ 20 mmHg
Pulse	<50 bpm	50-100 bpm	>100 bpm	≥ 10 bpm	≥ 30 bpm

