8.8.3 Vital Signs

Change in vital sign data will be classified as normal, low, high, based on a reference range. Observed and changes in vital sign parameters will be analyzed descriptively by time of collection and treatment group. Subjects with markedly abnormal changes will be listed and tabulated separately.

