### 11.3 Baseline and Change from Baseline

Baseline value is defined as the last non-missing value prior to the first dose of study drug. Change from baseline is defined as the post-baseline value minus the baseline value unless otherwise specified. Percent change from baseline is calculated as follows: Percent change = (Change from baseline / Baseline) \* 100.

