Baseline				
Observed Values				
N	XX	XX	XX	XX
Mean (SD)	XX.X (XX.X)	XX.X (XX.X)	XX.X (XX.X)	XX.X (XX.X)
Median	XX	XX	XX	XX
Minimum, Maximum	XX, XX	XX, XX	XX, XX	XX, XX
Week 4				
Observed Values				
N	XX	XX	XX	XX
Mean (SD)	XX.X (XX.X)	XX.X (XX.X)	XX.X (XX.X)	XX.X (XX.X)
Median	XX	XX	XX	XX
Minimum, Maximum	XX, XX	XX, XX	XX, XX	XX, XX
Change from Baseline				
N	XX	XX	XX	XX
Mean (SD)	XX.X (XX.X)	XX.X (XX.X)	XX.X (XX.X)	XX.X (XX.X)
Median	XX	XX	XX	XX
Minimum, Maximum	XX, XX	XX, XX	XX, XX	XX, XX

<Repeat for Week 8, Week 12, Week 16, Week 20, Week 24>

Note: Baseline is the last available measurement prior to the first dose of study drug on Day 1.

Generated on XX/XX/XX:XXXX by XXX / Uses: XXXX / Reference: Listing XXXX

Table 14.3.3.2: Summary of Vital Signs, Shifts from Baseline by Visit  
Safety Population  
[Pulse Rate (bpm)][ Systolic Blood Pressure (mmHg)][ Diastolic Blood Pressure (mmHg)]

	PPC-06 400 mg QD (N=XX)	PPC-06 400 mg BID (N=XX)	PPC-06 600 mg BID (N=XX)	Placebo (N=XX)
Baseline -> Week 4, n (%)				
N [1]	XX	XX	XX	XX
Low -> Normal	XX (XX.X)	XX (XX.X)	XX (XX.X)	XX (XX.X)
Normal -> Normal	XX (XX.X)	XX (XX.X)	XX (XX.X)	XX (XX.X)
High -> Normal	XX (XX.X)	XX (XX.X)	XX (XX.X)	XX (XX.X)
<Include all possible shifts as rows>				
Abnormal Change from Baseline	XX (XX.X)	XX (XX.X)	XX (XX.X)	XX (XX.X)
Markedly Abnormal Change from Baseline	XX (XX.X)	XX (XX.X)	XX (XX.X)	XX (XX.X)
Baseline -> Week 8, n (%)				
N [1]	XX	XX	XX	XX
Low -> Normal	XX (XX.X)	XX (XX.X)	XX (XX.X)	XX (XX.X)
Normal -> Normal	XX (XX.X)	XX (XX.X)	XX (XX.X)	XX (XX.X)
High -> Normal	XX (XX.X)	XX (XX.X)	XX (XX.X)	XX (XX.X)
<Include all possible shifts as rows>				
Abnormal Change from Baseline	XX (XX.X)	XX (XX.X)	XX (XX.X)	XX (XX.X)
Markedly Abnormal Change from Baseline	XX (XX.X)	XX (XX.X)	XX (XX.X)	XX (XX.X)

<continue with other visits: Week 12, Week 16, Week 20, Week 24>

Note: Pulse Rate: Low=<50bpm; Normal=50-100bpm; High=>100bpm; Abnormal change from baseline: >=10bpm; Markedly abnormal change from baseline: >=30bpm.

Systolic Blood Pressure: Low= <90mmHg; Normal= 90-140mmHg; High= >140mmHg; Abnormal change from baseline: >=20mmHg; Markedly abnormal change from baseline: >=40mmHg. Diastolic Blood Pressure: Low= <50mmHg; Normal= 50-90mmHg; High= >90mmHg; Abnormal change from baseline: >=10mmHg; Markedly abnormal change from baseline: >=20mmHg.

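### The vital-sign outlier rows pool large rises with large falls, which dilutes a one-directional effect, and the table footnote leaves the sign convention open

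*SAP*

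**What the plan says.** SAP 12.9.3 sets two change categories for systolic pressure, diastolic pressure and pulse. The columns are headed "Abnormal (Absolute) Change from Baseline" and "Markedly Abnormal (Absolute) Change from Baseline", and each holds one cut-off without a sign.

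Table 14.3.3.2 in SAP section 16 has one row for each category at each visit, the second labelled "Markedly Abnormal Change from Baseline". Its footnote repeats the cut-offs without the word absolute:

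- Systolic: "Abnormal change from baseline: >=20mmHg; Markedly abnormal change from baseline: >=40mmHg"
- Diastolic: "Abnormal change from baseline: >=10mmHg; Markedly abnormal change from baseline: >=20mmHg"
- Pulse: "Abnormal change from baseline: >=10bpm; Markedly abnormal change from baseline: >=30bpm"

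SAP 11.3 gives the general rule: "Change from baseline is defined as the post-baseline value minus the baseline value unless otherwise specified".

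Other planned outputs carry direction. Table 14.3.3.1 summarises change from baseline by arm and visit. Table 14.3.3.2 also has rows for every Low/Normal/High shift. Listing 16.2.8.4 prints each change from baseline, with L or H flags on the values.

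**The concern.** A drug that moves blood pressure or pulse one way makes large changes in that direction more common and large changes in the other direction less common. A row that adds the two shows only the difference between the gain and the loss. Flushing is among the most common adverse events reported for this product (Protocol 2.3), so a directional effect is worth being able to see. The documents themselves state no effect on blood pressure or pulse.

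The shift rows do not fill the gap. They register a change only when it crosses a fixed limit. A systolic fall from 138 to 98 mmHg is 40 mmHg, which meets the markedly abnormal cut-off, yet it stays within 90-140 mmHg and is tabulated as Normal to Normal.

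There is also a programming question. The footnote gives only a 'greater than or equal' cut-off, and 11.3 makes change signed by default. Someone working from the shell and 11.3 would count rises only and flag no falls.

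**Working it through.** The plan states no rate, power or precision for vital-sign outliers, so there is no figure of its own to reproduce. The calculation below shows how much of a one-directional effect the pooled row loses.

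**Inputs.** The cut-offs come from SAP 12.9.3: systolic 20/40 mmHg, diastolic 10/20 mmHg, pulse 10/30 bpm. The SD of change and the drug shift are assumptions, because the documents give neither.

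**Model.** Change is Normal with mean 0 on placebo, mean d on active and common SD s. Let c be the cut-off, Φ the standard normal distribution function and |d| the size of the shift.

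- Placebo, either tail: p = 1 − Φ(c/s)
- Active, tail in the direction of the drug effect: a = 1 − Φ((c − |d|)/s)
- Active, opposite tail: b = 1 − Φ((c + |d|)/s)
- Excess in the affected direction: a − p
- Excess in the pooled row: (a + b) − 2p
- Share offset: (p − b)/(a − p)

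**Diastolic, c = 10, s = 8, d = −4.** The z-values are 1.25, 0.75 and 1.75, so p = 10.6%, a = 22.7%, b = 4.0%. Falls increase by 12.1 points. The pooled row goes from 21.1% to 26.7%, or +5.5 points before rounding. Share offset: 6.56/12.10 = 54%.

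**Systolic, c = 20, s = 12, d = −6.** The z-values are 1.67, 1.17 and 2.17, so p = 4.8%, a = 12.2%, b = 1.5%. Falls increase by 7.4 points. The pooled row goes from 9.6% to 13.7%, or +4.1 points. Share offset: 3.27/7.39 = 44%.

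**Markedly abnormal cut-offs, same SDs and shifts.**

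- Diastolic, c = 20: p = 0.62%, a = 2.28%, b = 0.13%; share offset 0.486/1.654 = 29%.
- Systolic, c = 40: p = 0.043%, a = 0.230%, b = 0.006%; share offset 0.037/0.187 = 20%.

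**Pulse, s = 10, d = +5.** At c = 10 rises go from 15.9% to 30.8% (+15.0 points) and the pooled row from 31.7% to 37.5% (+5.8 points), 61% offset. At c = 30 the offset is 23%.

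**Range.** The grid is systolic SD 10, 12, 15 with shift 2, 5, 10; diastolic SD 7, 8, 10 with shift 2, 3, 5; pulse SD 8, 10, 12 with shift 2, 5, 8.

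| Parameter | Share offset, abnormal | Share offset, markedly abnormal |
|---|---|---|
| Systolic | 16% to 84% (≥20) | 2% to 70% (≥40) |
| Diastolic | 38% to 82% (≥10) | 14% to 67% (≥20) |
| Pulse | 32% to 87% (≥10) | 3% to 66% (≥30) |

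The share grows as the shift becomes small relative to the SD. In every case the pooled rate is still higher on active than on placebo.

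**Sign convention.** The 12.9.3 headings say absolute; the table footnote does not; 11.3 makes change signed unless stated otherwise. The example in Listing 16.2.8.4 puts the markedly abnormal symbol beside the change for a diastolic value flagged low, which fits falls being counted. The intention can be inferred, but the table shell does not state it.

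**The case against.** The strongest reply is that direction is already reported. Table 14.3.3.1 gives the mean, SD, median, minimum and maximum of signed change by arm and visit. A uniform shift, the only mechanism modelled above, is what a table of means shows best. With d = −4 and s = 8, the standard error of the difference between arms is 8 × √(2/100) = 1.13 mmHg at 100 per arm, so the shift is 3.5 standard errors. At the planned 50 completers per arm it is 1.6 mmHg and 2.5 standard errors. This stands: the safety report as a whole would not hide such an effect. It does not remove the point, because means do not count outliers, the minimum and maximum show one subject each, and the shift rows miss large changes within a band.

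Three stronger readings are tempting, and the documents do not support them.

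- *A directional effect is largely cancelled, or the rows have little ability to show one.* Roughly half the excess survives in the two blood-pressure examples at the lower cut-offs, and 70 to 80% at the markedly abnormal ones. Offsets above 80% arise only at the lower cut-offs, when the shift is small relative to the SD.
- *Falls are never flagged.* The listing example points the other way. The footnote is ambiguous, which is a lesser fault.
- *The SAP departs from the protocol.* Protocol 8.8.3 says "Change in vital sign data will be classified as normal, low, high, based on a reference range". SAP 12.9.3 repeats that sentence and supplies Low, Normal and High limits; the change cut-offs are an addition.

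**Conclusion.** The point holds as a minor one. The abnormal and markedly abnormal change rows are not split by direction, and no planned table counts large falls and large rises separately by arm. Under the two illustrative blood-pressure cases the pooled row loses about half the one-directional excess at the lower cut-offs and about 20 to 30% at the higher ones. These figures rest on a Normal model with a uniform shift and on assumed SDs and shifts. The share varies widely across plausible inputs, and cancellation is never complete. The tables are descriptive, so no inference or error rate is affected. Separately, the footnote to Table 14.3.3.2 needs to agree with 12.9.3, because as written it permits a rises-only count.

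**What to change.** In SAP 12.9.3 and Table 14.3.3.2, replace each change row by two rows, 'decrease ≥ threshold' and 'increase ≥ threshold', keeping the present cut-offs. Reword the table footnote to match, so that it is explicit that both directions are counted. Listing 16.2.8.4 needs no change, because it already prints the change from baseline.

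The cost is an edit to one SAP section and one table shell. No new data are needed, and the pooled count at each visit is the sum of the two new rows.
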